# **6.4.2.** Treatment(s) for Bleeding Episodes

Bleeding episodes that occur during this study may be treated (on-demand) with hemostatic therapy (recommend intravenous factor products for participants without inhibitors; rFVIIa bypass agent therapy at approximately 90 µg/kg and not to exceed a dosing frequency of every 2 hours for participants with inhibitors; or PCC at the lowest effective dose, in accordance with the Product Prescribing Information) as deemed appropriate by the investigator. The specific treatment with hemostatic therapy is at the discretion of the subject/caregiver/investigator, but all doses of hemostatic therapy taken after signing of informed consent will be documented as concomitant medications or concomitant treatments.

If a participant experiences a bleeding episode during the washout period preceding screening laboratory assessments, the participant is to be stabilized utilizing the participant's usual hemostatic treatment regimen. Once the bleeding episode has been successfully treated a new washout period should be completed prior to obtaining the screening laboratory tests.

If a participant experiences a bleeding episode during the washout period preceding the initial administration of PF-06741086 the participant is to be stabilized utilizing the participant's usual hemostatic treatment regimen and a new washout period should be implemented. Once treatment of the bleeding episode with hemostatic agents has been completed a new washout period should be initiated in anticipation of the initial treatment with PF-06741086.

If a participant experiences a bleeding episode during the PK assessment period following administration of PF-06741086, the participant is to be stabilized utilizing the Factor VIII or Factor IX treatment regimen at the lowest effective dose according to the approved Product Prescribing Information, or rFVIIa bypass agent therapy at approximately 90  $\mu$ g/kg and not to exceed a dosing frequency of every 2 hours, or PCC at the lowest effective dose, in accordance with the Product Prescribing Information, and protocol specified observations and procedures should proceed to completion.

If a participant experiences a bleeding episode after Day 28 following the initial administration of PF-06741086, the participant is to be stabilized utilizing the participant's usual hemostatic treatment regimen.

Treatment with aPCC or other plasma product (eg: Fresh frozen plasma or cyoprecipitate) in accordance with approved product labeling may be allowed only in the following scenarios in cases where such treatment is considered medically necessary during an emergency situation:

- rFVIIa provides insufficient control of participant's bleeding;
- in the absence of suitable hemostatic medication.

The use of hemostatic medications for bleeding episodes as specifically outlined in this Section (6.4.2) is not considered to be a protocol violation.

#### 6.5. Dose Modification

Not Applicable.

# 6.6. Intervention After the End of the Study

No intervention will be provided to study participants at the end of the study.

# 7. DISCONTINUATION OF STUDY INTERVENTION AND PARTICIPANT DISCONTINUATION/WITHDRAWAL

# 7.1. Discontinuation of Study Intervention

Since this is a single-dose study, this section is not applicable.

# 7.2. Participant Discontinuation/Withdrawal From the Study

A participant may withdraw from the study at any time at his own request. Reasons for discontinuation from the study include the following:

- Refused further follow-up;
- Lost to follow-up;
- Death;
- Study terminated by sponsor;

At the time of discontinuing from the study, if possible, an early discontinuation visit should be conducted. See the SoA (visit Day 7) for assessments to be collected at the time of study discontinuation and follow-up and for any further evaluations that need to be completed.

The early termination visit applies only to participants who are enrolled and then are prematurely withdrawn from the study. Participants should be questioned regarding their reason for withdrawal.

The participant will be permanently discontinued both from the study intervention and from the study at that time.

If a participant withdraws from the study, he may request destruction of any remaining samples taken and not tested, And the investigator must document any such requests in the site study records and notify the sponsor accordingly.

If the participant withdraws from the study and also withdraws consent (see Section 7.2.1) for disclosure of future information, no further evaluations should be performed and no additional data should be collected. The sponsor may retain and continue to use any data collected before such withdrawal of consent.

When a participant withdraws from the study because of an SAE, the SAE must be recorded on the CRF and reported on the Clinical Trial (CT) SAE Report.

The investigator should inquire about the reason for withdrawal, request that the participant return for a final visit, if applicable, and follow-up with the participant regarding any unresolved adverse events (AEs).

It may be appropriate for the participant to return to the clinic for final safety assessments to be scheduled as early as practically feasible following the decision to withdraw from the study. Participants should be questioned regarding their reason for withdrawal. At the early withdrawal visit, every effort must be made to complete the following assessments: Brief physical examination, if there is a new or open AE or clinically significant abnormal physical finding from the last visit;

- Assess heart rate, respiration rate, temperature and supine blood pressure;
- Single 12-lead ECG measurement (if ECG is abnormal, collect triplicate ECG);
- Obtain blood and urine samples for the following laboratory tests;
- Hematology (details in Table 6);
- Serum chemistry (details in Table 6);
- PT/INR;
- APTT;
- Anti-thrombin III;
- Fibrinogen:
- Cardiac Troponin I (only if withdrawal is prior to CRU discharge/Day 7);
- TFPI (total and free) levels;
- Thrombin Generation;
- Prothrombin fragment 1 + 2;
- D-dimer;
- Dilute prothrombin time (dPT);
- Urinalysis;
- Pharmacokinetic (PK) analysis;
- Immunogenicity (ADA, NAb).

Lack of completion of all or any of the withdrawal/early termination procedures will not be viewed as protocol deviations so long as the participant's safety was preserved.

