- a. The full physical examination (PE) planned for Screening may be performed on Day -1 before dosing at the discretion of the Investigator. If a full PE is done at Screening visit, then a brief PE is to be conducted on Day-1. After Day -1, brief examinations based on signs and symptoms will be performed if clinically indicated at the discretion of the Investigator to assess changes from baseline/previous visits of any ongoing symptoms.
- b. Vital signs to be assessed include pulse rate, respiration rate, temperature, and supine blood pressure.
- c. Differential hematology panel required at Screening, Day 1, and Day 7. Differential is optional at additional timepoints, as clinically indicated.
- d. Participants must be fasting for 12 hours prior to blood draw.
- e. A single sample to measure FVIII or FIX activity is to be collected after minimum washout period completed for prescribed factor-replacement product: FVIII replacement therapy for at least 72 hours; Extended half-life FVIII replacement therapy for at least 4× half-life; FIX replacement therapy for at least 4× half-life; bypass agent therapy from rFVIIa, prothrombin complex concentrate (PCC) or activated prothrombin complex concentrate (aPCC) for at least 72 hours.
- CD4 cell count test if HIV positive.
- g. Triplicate ECGs will be obtained at baseline pre-dose on Day 1. Single ECGs will be required at all additional timepoints unless ECG or troponin I is abnormal, in which case a triplicate ECG is required.
- PD blood sample including assessments for: Tissue factor pathway inhibitor (TFPI) (total and free), Thrombin Generation Assay (TGA), Prothrombin fragment 1+2 (PF1+2),
   D-dimer, Dilute prothrombin time (dPT).
- i. Participants with positive ADA results may be requested to return for additional follow-up visits after final planned follow-up visit.
- j. The follow-up Visit at Day 42 could be a Phone Follow-Up visit or a face to face clinic visit at the discretion of the investigator.
- k. Assessments for study early discontinuation or termination refer to Day7 visit. To note that cTnI should be assessed if discontinuation/termination occurs prior to Day 4. ADA and NAb sample will be also collected in case of study early discontinuation or termination.

PF-06741086 B7841010 Final Protocol Amendment 1 22-Oct-2020

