# 3. OBJECTIVES AND ENDPOINTS

Ob	jectives	Endpoints
Pri	mary:	Primary:
	To determine the safety and tolerability of a single SC dose of PF-06741086 administered to Chinese adult participants with severe hemophilia A or B with or without inhibitors.	• Frequency, severity and causal relationship of treatment emergent adverse events (TEAEs) and withdrawals due to TEAE; Day 1 up to Day 42.
		• Frequency and magnitude of abnormal laboratory findings (including hematology, PT/INR, APTT, chemistry, urinalysis, fibrinogen, ATIII activity and cardiac troponin I); Day 1 up to Day 28.
		Changes from baseline in vital signs (blood pressure, pulse rate, temperature and respiration rate) measurements 12-lead electrocardiogram (ECG) parameters and physical examination; Day 1 up to Day 28.
		• Frequency, severity and causal relationship of injection site reactions; Day 1 up to Day 7.
Sec	condary:	Secondary:
•	To characterize the PK profile of a SC single dose of PF-06741086.	
 
Plasma PF-06741086 concentrations as determined by a validated assay Day 1 up to Day 28, and noncompartmental PK parameters including Cmax, Tmax, AUClast, AUCinf, terminal half-life, Vz/F, CL/F.
 

•	To characterize the PD profile of a SC single dose of PF-06741086.	• TFPI (total and free); Thrombin generation (including lag time, peak thrombin generation and endogenous thrombin generation potential); Prothrombin fragment 1+2 (PF 1+2); D-dimer; Dilute prothrombin time (dPT); Day 1 up to Day 28.
•	To characterize the immunogenicity of a single SC dose of PF-06741086.	Frequency of anti-drug antibody (ADA) and neutralizing antibody (NAb) production against PF-06741086; Day 1 up to Day 28. Only positive ADA samples and the corresponding baseline sample will be tested in the NAb assay.

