#### 7.2.1. Withdrawal of Consent:

Participants who request to discontinue receipt of study treatment will remain in the study and must continue to be followed for protocol specified followup procedures. The only exception to this is when a participant specifically withdraws consent for any further contact with him or her or persons previously authorized by the participant to provide this information.

Participants should notify the investigator in writing of the decision to withdraw consent from future follow-up, whenever possible. The withdrawal of consent should be explained in detail in the medical records by the investigator, as to whether the withdrawal is only from further receipt of investigational product or also from study procedures and/or posttreatment study follow-up, and entered on the appropriate CRF page. In the event that vital status (whether the participant is alive or dead) is being measured, publicly available information should be used to determine vital status only as appropriately directed in accordance with local law.

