## 8.3.1. Time Period and Frequency for Collecting AE and SAE Information

The time period for actively eliciting and collecting AEs and SAEs ("active collection period") for each participant begins from the time the participant provides informed consent, which is obtained before the participant's participation in the study (ie, before undergoing any study related procedure and/or receiving investigational product), through and including a minimum of 42 calendar days after the last administration of the study intervention.

Follow-up by the investigator continues throughout and after the active collection period and until the AE or SAE or its sequelae resolve or stabilize at a level acceptable to the investigator, and Pfizer concurs with that assessment.

For participants who are screen failures, the active collection period ends when screen failure status is determined.

If the participant withdraws from the study and also withdraws consent for the collection of future information, the active collection period ends when consent is withdrawn.

If a participant definitively discontinues or temporarily discontinues study intervention because of an AE or SAE, the AE or SAE must be recorded on the CRF and the SAE reported using the CT SAE Report Form.

Investigators are not obligated to actively seek AEs or SAEs after conclusion of the study participation. However, if the investigator learns of any SAE, including a death, at any time after a participant has been discharged from the study, and he/she considers the event to be reasonably related to the study intervention, the investigator must promptly report the SAE to Pfizer using the CT SAE Report Form..

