#### 9.1. Estimands and Statistical Hypotheses

There are no statistical hypotheses and estimands are not applicable.

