# 9.2. Sample Size Determination

Sample size of 6 is not determined based on statistical considerations. The size of 6 is based on Chinese patients

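### For a dosed participant who leaves without withdrawing consent, Protocol 7.2 and 8.3.1 disagree on whether adverse events are still collected to Day 42, so the primary TEAE endpoint may be under-counted

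*Protocol*

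**What the plan says.** The first primary endpoint in Protocol 3 is "Frequency, severity and causal relationship of treatment emergent adverse events (TEAEs) and withdrawals due to TEAE; Day 1 up to Day 42". SAP 3.1 repeats it.

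Protocol 8.3.1 runs active collection for every participant from consent "through and including a minimum of 42 calendar days after the last administration of the study intervention". It names two early ends. One is for screen failures. The other is for a participant who withdraws from the study and also withdraws consent to future information, in which case "the active collection period ends when consent is withdrawn". The same section adds that investigators need not actively look for events once study participation has concluded. After that, only an SAE that the investigator happens to learn of and considers related must be reported.

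Protocol 7.2 asks for one early discontinuation visit where feasible and then says: "The participant will be permanently discontinued both from the study intervention and from the study at that time". Consent withdrawal has its own paragraph there, so the release also covers men who have not withdrawn consent. Footnote k of the Schedule of Activities sets the visit content: "Assessments for study early discontinuation or termination refer to Day7 visit". It adds ADA/NAb samples, and troponin for exits before Day 4. After exit, 7.2 asks for follow-up of unresolved AEs.

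Protocol 7.2.1 says that participants who ask to stop treatment "will remain in the study and must continue to be followed for protocol specified followup procedures", unless they withdraw consent to contact.

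SAP 4 defines the Safety set as all enrolled participants who were dosed. SAP 5.2 reports numbers and percentages.

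**The concern.** The single dose is given on Day 1, so a participant who leaves on Day 10 has had the whole exposure. Leaving changes only what is observed. Two sections give a site different grounds for deciding whether to contact him again, and neither says which prevails.

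The late part of the window is not empty of interest. Protocol 2.2.3.3.1 reports that several PD effects last beyond 7 days after 300 mg SC. Protocol 2.3 names thrombi or emboli and ADA-induced hypersensitivity as potential risks, and post-dose immunogenicity sampling starts only on Day 14.

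At stake is the completeness of a primary safety endpoint in a very small study. The Day 1 to Day 42 bleeding summary in SAP 6.5.4 has the same gap.

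**Working it through.** **Reading the passages together**

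1. Under 8.3.1, collection for a dosed participant who has not withdrawn consent stays open for at least 42 days after dosing.
2. Under 7.2, the same participant is out of the study at exit.
3. The sentence in 8.3.1 on concluded participation connects the two: once 7.2 ends participation, a site can stop asking without obviously breaching 8.3.1.
4. What remains after exit is follow-up of unresolved AEs (7.2), follow-up of treatment-related AEs (4.1), and reporting of related SAEs that come to the investigator's notice (8.3.1). New non-serious AEs, and SAEs not judged related, have no stated route.

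**Who is affected**

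- Of the reasons listed in 7.2, death and loss to follow-up leave nothing to collect, and refusal of further follow-up is close to withdrawal of consent.
- The list is not exhaustive. Protocol 6.4 leaves continued participation after a prohibited medication to a case-by-case decision. Protocol 6.4.1 allows withdrawal after rFVIIa use beyond its stated limits. Sponsor termination is also listed in 7.2. In these cases the participant has refused nothing.

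**Size**

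There is no planned figure to reproduce: "Sample size of 6 is not determined based on statistical considerations", and "There are no statistical hypotheses and estimands are not applicable".

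Inputs from the documents: N = 6; endpoint window to Day 42; all dosed participants in the denominator. Assumed, because the documents give no figures: w = 1 or 2 exits at Day 7, true Day 42 risk p of any TEAE from 10% to 70%, constant hazard, and no event captured after exit.

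- Upper bound for one exit with no earlier TEAE: an observed x/6 could truly be (x + 1)/6. The difference is 1/6 = 16.7 points.
- Calendar days after exit: 42 − 7 = 35 for a Day 7 exit; 42 − 14 = 28 for Day 14; 42 − 28 = 14 for Day 28.
- Risk observed before exit at day t: 1 − (1 − p)^(t/42).
- Expected crude percentage: [(6 − w)·p + w·(1 − (1 − p)^(t/42))]/6.
- Example with p = 0.5, t = 7, w = 1: the observed part is 1 − 0.5^(7/42) = 0.109. The crude value is (5 × 0.5 + 0.109)/6 = 0.435, an understatement of 6.5 points.

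| True Day 42 risk | One Day 7 exit | Two Day 7 exits |
|---|---|---|
| 10% | 1.4 points | 2.8 points |
| 30% | 4.0 points | 8.1 points |
| 50% | 6.5 points | 13.0 points |
| 70% | 8.6 points | 17.3 points |

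Later exits cost less. At p = 0.5, one exit at Day 14 gives 4.9 points and one at Day 28 gives 2.2.

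**The case against.** The best defence is that the sections can be read as one rule. Protocol 7.2 never says that AE collection stops. Its only explicit bar on further data applies when consent is also withdrawn, the same two-part condition as in 8.3.1. It points to the Schedule of Activities for follow-up, where AE, bleeding and medication rows run to Day 42. Protocol 7.3 requires contact with anyone who merely misses visits. This stands in part: the text is ambiguous and does not order sites to stop. It does not remove the problem, because 7.2 ends participation and 8.3.1 ties the duty to seek events to participation.

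A reader might infer that 7.2.1 is a third competing rule. It is not: it concerns stopping treatment, and after a single dose there is none left to stop, as 7.1 recognises.

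A reader might also infer that the SAP counts such a man as event-free. Neither document says so. It follows from the Safety-set denominator and crude percentages, and SAP 5.3 refers to sponsor imputation rules that it does not state. For the any-TEAE percentage it could apply only if he had no TEAE before exit.

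Finally, calendar share is not risk share. Losing 35 of 42 days (83%) overstates the loss if risk is front-loaded. Protocol 2.2.3.2.1 gives an SC peak at 48 to 108 hours, and its longest mean half-life in non-Japanese participants is 79.5 hours (440 mg IV), so five half-lives are 397.5 hours, about 17 days. One Japanese participant had 122 hours. Participants are also confined to Day 7, withdrawals due to TEAEs are part of the endpoint, and SAP 6.5.6 summarises discontinuations with reasons. All of this stands, and it limits the severity.

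**Conclusion.** The inconsistency is real and in current text, for a small group: dosed participants who leave or are withdrawn without withdrawing consent to further contact. For them the Day 1 to Day 42 TEAE endpoint may be under-counted while they remain in the denominator.

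The maximum effect of one such exit on the any-TEAE percentage is 16.7 points. The expected effect of one Day 7 exit is about 1.4 to 8.6 points. That range rests on an assumed true risk of 10% to 70%, a constant hazard and no capture after exit; if early risk is higher than late risk, the loss is smaller. How likely any exit is cannot be judged, because no dropout rate is given.

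The documents do not support the stronger readings that sites are told to stop collecting AEs, or that the SAP prescribes counting these men as event-free. In a descriptive study of about six participants the severity is minor to moderate.

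**What to change.** **Protocol 7.2 and Schedule of Activities footnote k:** reconcile them with 8.3.1. State that, unless a dosed participant withdraws consent to further contact, collection of AEs/SAEs, bleeding episodes and concomitant medication continues to the final Day 42 contact. Footnote j already lets that contact be by telephone. An extra Day 28 call is not needed.

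**SAP 6.1:** beside the TEAE summary, list the last AE contact day for each participant who stopped early, so that a reader can see how much of the window was observed.

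**Cost:** protocol and SAP wording, and about one telephone call per withdrawn participant. No new procedure is needed.

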#### 7.2.1. Withdrawal of Consent:

Participants who request to discontinue receipt of study treatment will remain in the study and must continue to be followed for protocol specified followup procedures. The only exception to this is when a participant specifically withdraws consent for any further contact with him or her or persons previously authorized by the participant to provide this information.

Participants should notify the investigator in writing of the decision to withdraw consent from future follow-up, whenever possible. The withdrawal of consent should be explained in detail in the medical records by the investigator, as to whether the withdrawal is only from further receipt of investigational product or also from study procedures and/or posttreatment study follow-up, and entered on the appropriate CRF page. In the event that vital status (whether the participant is alive or dead) is being measured, publicly available information should be used to determine vital status only as appropriately directed in accordance with local law.

## 7.3. Lost to Follow-up

A participant will be considered lost to follow-up if they repeatedly fail to return for scheduled visits and is unable to be contacted by the study site.

The following actions must be taken if a participant fails to return to the clinic for a required study visit:

- The site must attempt to contact the participant and reschedule the missed visit as soon as possible and counsel the participant on the importance of maintaining the assigned visit schedule and ascertain whether or not the participant wishes to and/or should continue in the study;
- Before a participant is deemed lost to follow-up, the investigator or designee must make every effort to regain contact with the participant (where possible, 3 telephone calls and, if necessary, a certified letter to the participant's last known mailing address or local equivalent methods). These contact attempts should be documented in the participant's medical record;
- Should the participant continue to be unreachable, they will be considered to have withdrawn from the study.

Discontinuation of specific sites or of the study as a whole is handled as part of Appendix 1.

